#### Serious Adverse Event

A serious adverse event is any untoward medical occurrence that meets the above definition and any of the following conditions:

- results in death;
- is life threatening (places the subject at immediate risk of death from the event as it occurred);
- requires inpatient hospitalization or prolongation of existing hospitalization;
- results in a persistent or significant disability/incapacity;
- results in a congenital anomaly/birth defect; or
- any other adverse event that, based upon appropriate medical judgment, may jeopardize the subject's health and may require medical or surgical intervention to prevent one of the outcomes listed above (examples of such events include allergic bronchospasm requiring intensive treatment in the emergency room or at home, blood dyscrasias or convulsions that do not result in inpatient hospitalization, or the development of drug dependency or drug abuse).

Note: Medical and scientific judgment should be exercised in deciding whether expedited reporting is appropriate in other situations; for example, important medical events may not be immediately life-threatening or result in death or hospitalization, but may jeopardize the subject or may require intervention to prevent one of the outcomes listed in the definition above.

#### Unexpected (Unlisted) Adverse Event

- Any adverse event occurring in one or more subjects participating in a research protocol, the nature, severity, or frequency of which is not consistent with either:
- the known or foreseeable risk of adverse events associated with the procedures involved in the research that are described in (a) the protocol-related documents, such as the IRB-approved research protocol, any applicable investigator brochure,

and the current IRB-approved informed consent document, and (b) other relevant sources of information, such as product labeling and package inserts; or

- the expected natural progression of any underlying disease, disorder, or condition of the subject(s) experiencing the adverse event and the subject's predisposing risk factor profile for the adverse event.

#### Associated with the Use of the Drug

An adverse event is considered associated with the use of the drug if the attribution is possible, probable or very likely by the definitions listed below:

#### Attribution Definitions

- **Not related** An adverse event which is not related to the use of the drug.
- **Doubtful** An adverse event for which an alternative explanation is more likely, e.g., concomitant drug(s), concomitant disease(s), and/or the relationship in time suggests that a causal relationship is unlikely.
- **Possible** There is a reasonable possibility that the adverse event, incident, experience or outcome may have been caused by the procedures involved in the research (modified from the definition of associated with use of the drug in FDA regulations at 21 CFR 312.32(a)). A reasonable possibility is defined as more likely than not related to the research procedures or, in other words, there is a > 50% likelihood of the event having been caused by the procedures involved in the research.
- **Probable** An adverse event which might be due to the use of the drug. The relationship in time is suggestive (e.g., confirmed by dechallenge). An alternative explanation is less likely, e.g., concomitant drug(s), concomitant disease(s).
- **Very likely** An adverse event which is listed as a possible adverse reaction and cannot be reasonably explained by an alternative explanation, e.g., concomitant drug(s), concomitant disease(s). The relationship in time is very suggestive (e.g., it is confirmed by dechallenge and rechallenge).

#### **All Adverse Events**

All adverse events that occur between the first study-related procedure and within 30 days of the last dose of study medication will be reported. Adverse events will be reported to the PHRC according to their guidelines.

Subjects should report any adverse events voluntarily or in response to general, non-directed questioning (e.g., "How has your health been since the last visit?). For each adverse event reported by the subject, the investigator should obtain all the information required to complete documentation in the subject's research file.

All adverse events, regardless of seriousness, severity, or presumed relationship to study therapy, must be recorded using medical terminology in the subject's study documents. Whenever possible, diagnoses should be given when signs and symptoms are due to a common etiology (e.g., cough,

runny nose, sneezing, sore throat, and head congestion should be reported as “upper respiratory infection”). The investigator must document his/her opinion concerning the relationship of the adverse event to study therapy. All measures required for adverse event management must be recorded in the source document.

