### **OVERVIEW OF STUDY DESIGN**

This is a single center, 13-week, outpatient, randomized, double-blind, placebo-controlled, parallel group, pilot study of topiramate in subjects with Sleep-Related Eating Disorder.

After giving informed consent, subjects who meet all the inclusion and exclusion criteria may be enrolled. The study will consist of two phases:

- pre-randomization phase (up to 56 days prior to randomization), consisting of a screening/washout period (up to 42 days) and a prospective baseline period (14 days);
- treatment phase, consisting of titration period: up to 9 weeks; maintenance period: 4 weeks; taper period: 2 weeks.

The study medication will be titrated to 300 mg/day or the subject's minimum effective dose. Subjects must reach a minimum dose of 25 mg/day after the second week of titration. The taper period will last approximately two weeks during which subjects will gradually reduce their medication until they are no longer taking the study medication.

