### **Titration Schedule \***

Double-Blind Topiramate / Placebo Dosing				
Days	Study Medication		Total Daily Dose	
	25 mg Tablets	100 mg Tablets	Topiramate	Placebo
1-7	1 capsule		25 mg	Matching capsules
8-14	2 capsules		50 mg	
15-21	3 capsules		75 mg	
22-28	4 capsules		100 mg	
29-35	5 capsules		125 mg	
36-42	6 capsules		150mg	
43-49		2 capsules	200mg	
50-56	2 capsules	2 capsules	250 mg	
57+		3 capsules	300 mg	

Subjects will be instructed to take the study medication one hour prior to bedtime (h.s.). Subjects will be informed during the consent process that they may be asked to take up to six pills at different points during the titration period. The study medication will be titrated to 300 mg/day or the subject's minimum effective dose (MED).

At the investigator's discretion the titration rate may be adjusted. However, after the second week of titration, subjects must take at least 25 mg/day of topiramate or matching placebo for the duration of the double-blind phase. During the maintenance period, subjects should remain at the dose attained at the end of the titration period, however dose adjustments will be permitted at the discretion of the investigators.

Subjects will taper their study medication by decreasing the dose by approximately 30% every three days over approximately a 14-day period until they are no longer taking study medication.

\*Subjects with an estimated creatinine clearance <70 but >60 will be included in the study, but will follow a modified titration schedule. Dose increases for these subjects will be take place no less than every 14 days rather than every 7 days, and at the end of the titration period they will reach a maximum dose of 125mg. During the maintenance period, subjects should remain at the dose attained at the end of the titration period, however dose adjustments will be permitted at the discretion of the investigators up to a maximum dose of 150mg.

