### **Taper Period**

After completion of the titration and maintenance periods (13 weeks), subjects will taper their study medication by decreasing their dose by approximately 30% every three days. Subjects will return for Visit 9 (Day 105) and the following procedures will be performed:

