#### **Visit 9 (Day 105)**

1. Assess concomitant medications
2. Obtain weight
3. Record adverse events
4. Collect study medication and perform drug accountability

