### **Early Withdrawal**

Subject participation may be terminated based upon subject choice, protocol violation (e.g., non-compliance), adverse event, or if a subject is lost to follow-up. The primary reason for withdrawal should be clearly indicated in the subject's study file.

In the event that a subject discontinues prematurely, final visit procedures will be performed at the time of discontinuation, if possible. Subjects who discontinue prematurely should be scheduled promptly for final visit (Visit 8, Day 91) procedures, preferably within 24 hours of the last dose. Subjects should taper study medication as discussed under Study Treatments. All adverse events should be followed to resolution, if possible. All unused study medication must be returned to the investigator.

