### TIME AND EVENTS SCHEDULE

	Visit 1A (Day -56)	Visit 1 (Day -14)	Visit 2 (Day 1)	Visit 3 (Day 7)	Phone Contact (Day 14)	Visit 4 (Day 21)	Phone Contact (Day 28)	Visit 5 (Day 35)	Phone Contact (Day 42)	Visit 6 (Day 49)	Phone Contact (Day 56)	Visit 7 (Day 63)	Phone Contact (Day 77)	Visit 8 (Day 91)	Visit 9 (Day 105)
Informed Consent	X														
Review Inclusion/Exclusion Criteria	X	X	X												
Concomitant Medication Review	X	X	X	X	X	X	X	X	X	X	X	X	x	X	X
Medical & Psychiatric History	X														
Physical Examination	X														
Neurologic Examination	X														
SCID Eating Disorders	X														
Weight	X	X	X	X		X		X		X		X		X	X
Urine Pregnancy Test		X						X				X			
Urine Drug Screen		X													
Blood HbA1C		X*												X	
MOS			X					X				X		X	
Epworth Sleepiness Scale			X					X				X		X	
HAM-D	X							X				X		X	
TFEQ		X												X	
EAT	X														
Sheehan Disability Scale		X												x	
Dispense Sleep and Night- Eating Diary		X	X	X		X		X		X		X			
Review Sleep and Night- Eating Diary			X	X	X	X	X	X	x	X	x	X	X	X	
Record Adverse Events		X	X	X	X	X	X	X	X	X	X	X	X	X	X
Dispense Study Medication			X	X	X	X	X	X	x	X	x	X	x	X	
Collect study medication and perform drug accountability				x		x		X		X		X		x	X

\*Creatinine also tested at visit 1

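### The 30-day adverse-event window runs about 25 to 30 days past the last scheduled contact (Visit 9), and the plan does not say whether early withdrawals attend that visit

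*Combined protocol and SAP*

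**What the plan says.** All Adverse Events sets the reporting window: all events "between the first study-related procedure and within 30 days of the last dose of study medication will be reported". It names two routes for learning of an event, the subject's own report and open questioning by staff.

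The treatment schedule is in three places. The Taper Period section says "After completion of the titration and maintenance periods (13 weeks), subjects will taper their study medication". The text under the titration table describes "decreasing the dose by approximately 30% every three days over approximately a 14-day period until they are no longer taking study medication". The design overview likewise gives a taper of about two weeks, ending at zero dose.

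The Taper Period section then says "Subjects will return for Visit 9 (Day 105) and the following procedures will be performed". The Visit 9 list includes "Record adverse events". Visit 9 is the last column of the Time and Events Schedule, and the "Record Adverse Events" row ends there. No later visit or call is listed. Once a subject is on study drug, visits may move by 3 days either way (Study Evaluations, General Considerations).

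For those who stop early, Early Withdrawal says "Subjects who discontinue prematurely should be scheduled promptly for final visit (Visit 8, Day 91) procedures", preferably within a day of the last dose. It also asks for a taper and for events to be followed until they resolve where possible. It does not mention Visit 9. Items 13 and 14 of the Visit 8 list, however, dispense taper medication and book a post-taper Visit 9 about two weeks later.

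**The concern.** Safety is part of the primary objective. From Visit 1 on, every visit and call includes the recording of adverse events, so each contact covers the period since the one before. That chain ends at Visit 9, at or shortly after the last taper dose, while the stated window continues for weeks. Events in that stretch would reach the investigator only if the subject volunteered them or if they belonged to an event already being followed. A single adverse-event table could then combine two methods of collection under one stated window.

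Two features of the plan add to this. The attribution scale uses dechallenge as its example of supportive timing for the two strongest categories, and dechallenge needs observation off drug. The Safety Analyses section tabulates treatment-emergent events without defining the period, so the 30 days is the only end point a reader could apply.

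**Working it through.** **Inputs.** Visit 8 on Day 91; taper of about 14 days in steps of about 30% every three days; Visit 9 on Day 105, give or take 3 days; window end = last dose + 30 days. Visit 8 is held at Day 91 throughout.

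**Step 1, the plan's own figure.** 91 + 14 = Day 105, which matches the stated day of Visit 9. On the nominal schedule, Visit 9 falls on about the day of the last dose.

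**Step 2, when the last dose falls.** The taper wording allows more than one reading.
- Cuts of 30% of the starting dose give levels of 70%, 40% and 10%, three days each. If the first cut is on Day 92 the last dose is on Day 100; if it is on Day 95, Day 103.
- Cuts of 30% of the current dose give 0.7^4 = 24.0% on Days 101 to 103 and 0.7^5 = 16.8% on Days 104 to 106. This never reaches zero by itself, so the 14-day length sets the end, at about Day 105.

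**Step 3, days without a scheduled contact** = window end − day of Visit 9.

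| Last dose | Window closes | Visit 9 on Day 105 | Visit 9 on Day 102 | Visit 9 on Day 108 |
|---|---|---|---|---|
| Day 100 | Day 130 | 25 | 28 | 22 |
| Day 103 | Day 133 | 28 | 31 | 25 |
| Day 105 | Day 135 | 30 | 33 | 27 |

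With Visit 9 on Day 105, 25 to 30 days are uncovered and the visit falls 0 to 5 days after the last dose. Across the table the range is 22 to 33 days.

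**Step 4, early withdrawals.** Count from the last full dose as day 0. Visit 8 procedures fall on day 0 or 1. With a taper of about 14 days, the window closes at 14 + 30 = day 44.
- If the post-taper visit takes place at about day 14: 44 − 14 = 30 days uncovered.
- If Early Withdrawal is read as ending with the Visit 8 procedures: 44 − 1 = 43 to 44 − 0 = 44 days uncovered.
- If no taper is taken, the window closes at day 30 and 29 to 30 days are uncovered after the Visit 8 procedures.

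**Step 5, the meaning of last dose.** Early Withdrawal places the Visit 8 procedures within a day of the last dose and then calls for a taper. There the term seems to mean the last full dose. In All Adverse Events it refers to study medication generally, which would include taper doses. The two sections and the Visit 8 list need to be reconciled before the window has one end date for these subjects.

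**The case against.** The strongest reply is that the plan sets a reporting window and does not promise active follow-up to its end. Voluntary report is one of its two named routes. That is a fair reading of the wording, and a reader should not infer that the protocol promises a 30-day visit. It does not close the gap: up to Visit 9 events are prompted at each contact, and after it nothing prompts them. The documents supplied contain no instruction to subjects about reporting in that period.

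Second, the stated half-life is 21 hours, so 30 days is 720/21, or about 34 half-lives, and late drug-related events may be few. The taper itself is covered by Visit 9. Both points stand as limits on the likely harm. But on the nominal schedule Visit 9 coincides with the last dose, so the first days off drug are also unobserved. At most, with a last dose on Day 100, Visit 9 on Day 105 is 120/21, or about 5.7 half-lives, later.

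Third, the gap applies to both arms alike, and nothing in the documents shows a bias between them. That stands. The supportable statement is that events may be missed, not that they will be or that the comparison is distorted.

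A reader might also infer that early withdrawals have no contact at all after the Visit 8 procedures. The documents do not support that: those procedures include booking the post-taper visit, and known events are to be followed to resolution where possible. Nor can the number of early withdrawals be taken from the 17-patient case series in the background. All 17 took topiramate, without a control group, and of the 6 who stopped, 4 did so for lack of efficacy and only 2 for side effects.

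**Conclusion.** The point holds. Followed as written, the schedule cannot systematically deliver the stated window. For completers the shortfall is about 25 to 30 days with Visit 9 on Day 105, assuming Visit 8 on Day 91 and one of the taper readings shown. No reading examined brings it below 22 days. For early withdrawals who taper, it is about 30 days if Visit 9 applies and about 43 to 44 if it does not; the larger figure is the worst-case reading only. Efficacy analyses are unaffected. The number of events that would be missed cannot be estimated from the documents.

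**What to change.** Add one telephone contact about 30 days after the last dose (about Day 135 for completers on the nominal schedule) for every randomised subject, including early withdrawals. It should carry the adverse-event and concomitant-medication items, and have its own column in the Time and Events Schedule. State in Early Withdrawal whether Visit 9 applies. Reconcile that section, the Visit 8 list and All Adverse Events on which dose counts as the last for the reporting window.

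The cost is about 40 short calls, one for each of the 40 subjects planned for randomisation, and an amendment. The trial already makes calls of this kind, and phone calls carry no compensation under the Compensation section.

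If no call is added, the report should say that adverse events were actively collected only to Visit 9, or to the last contact for early withdrawals, and only by voluntary report after that. This costs wording alone, but leaves the gap in the data.

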### **Pregnancies**

Pregnancies occurring during the study will be reported by the investigational staff within one working day of their knowledge of the event. Any subject who becomes pregnant during participation in this study will be promptly withdrawn from the study. Follow-up information regarding the outcome of the pregnancy and any postnatal sequelae in the infant will be required.

### **Compensation**

Subjects will be compensated \$30.00 for each study visit, for a total of up to \$300.00 for those who complete the entire study. Subjects will not be compensated for phone calls.

## **STATISTICAL METHODS**

### **Sample Size Determination**

The sample size for this pilot study was not based upon statistical considerations.

### **Efficacy Analyses**

The efficacy analyses will be performed on an intent-to-treat (ITT) population defined as all randomized subjects who were dispensed study medication and for whom one post-baseline efficacy measurement is available.

Efficacy analyses will be conducted separately for subjects with night eating syndrome or sleep-related eating disorder, and across all subjects with either of these two diagnoses. The primary efficacy parameter will be the change in the number of nights per week of the specified nocturnal eating episode.

The primary efficacy parameter of number of nights per week with nocturnal episodes will be analyzed using ANCOVA with baseline frequency of nocturnal episodes as a co-variate. Diagnostic procedures will be conducted to determine whether the statistical assumptions are met.

The MOS, SDS, TFEQ, HAM-D, HbA1C, body weight and Epworth Sleepiness Scale will be analyzed using an ANCOVA with the baseline value as a covariate.

Information obtained from the sleep diaries will be summarized.

### **Safety Analyses**

#### **Adverse Events**

The percent of subjects with specific treatment-emergent adverse events will be summarized by treatment group.

Additional tabulations will be conducted to summarize those subjects who have discontinued treatment due to an adverse event or who experienced a severe or a serious adverse event.

#### **Clinical Laboratory Tests**

Laboratory data will be summarized by treatment group by the type of laboratory test.

### TIME AND EVENTS SCHEDULE

	Visit 1A (Day -56)	Visit 1 (Day -14)	Visit 2 (Day 1)	Visit 3 (Day 7)	Phone Contact (Day 14)	Visit 4 (Day 21)	Phone Contact (Day 28)	Visit 5 (Day 35)	Phone Contact (Day 42)	Visit 6 (Day 49)	Phone Contact (Day 56)	Visit 7 (Day 63)	Phone Contact (Day 77)	Visit 8 (Day 91)	Visit 9 (Day 105)
Informed Consent	X														
Review Inclusion/Exclusion Criteria	X	X	X												
Concomitant Medication Review	X	X	X	X	X	X	X	X	X	X	X	X	x	X	X
Medical & Psychiatric History	X														
Physical Examination	X														
Neurologic Examination	X														
SCID Eating Disorders	X														
Weight	X	X	X	X		X		X		X		X		X	X
Urine Pregnancy Test		X						X				X			
Urine Drug Screen		X													
Blood HbA1C		X*												X	
MOS			X					X				X		X	
Epworth Sleepiness Scale			X					X				X		X	
HAM-D	X							X				X		X	
TFEQ		X												X	
EAT	X														
Sheehan Disability Scale		X												x	
Dispense Sleep and Night- Eating Diary		X	X	X		X		X		X		X			
Review Sleep and Night- Eating Diary			X	X	X	X	X	X	x	X	x	X	X	X	
Record Adverse Events		X	X	X	X	X	X	X	X	X	X	X	X	X	X
Dispense Study Medication			X	X	X	X	X	X	x	X	x	X	x	X	
Collect study medication and perform drug accountability				x		x		X		X		X		x	X

\*Creatinine also tested at visit 1

**Attachment 1**  
**Medical Outcome Study (MOS) Sleep Scale**

1. How long did it usually take you to fall asleep during the past 4 weeks? (circle one)

- |                           |   |
|---------------------------|---|
| 0-15 minutes.....         | 1 |
| 16-30 minutes.....        | 2 |
| 31-45 minutes.....        | 3 |
| 46-60 minutes.....        | 4 |
| More than 60 minutes..... | 5 |

2. On the average, how many hours did you sleep each night during the past 4 weeks?

Write in # of hours per night \_\_\_\_\_

How often during the past 4 weeks did you.... (circle one number on each line):

	All of the Time	Most of the Time	A Good Bit of the Time	Some of the Time	A Little of the Time	None of the Time
3. feel that your sleep was not quiet (moving restlessly, feeling tense, speaking, etc., while sleeping)?	1	2	3	4	5	6
4. get enough sleep to feel rested upon waking in the morning?	1	2	3	4	5	6
5. awoken short of breath or with a headache?	1	2	3	4	5	6
6. feel drowsy or sleepy during the day?	1	2	3	4	5	6
7. have trouble falling asleep?	1	2	3	4	5	6
8. awoken during your sleep time and have trouble falling asleep again?	1	2	3	4	5	6
9. have trouble staying awake during the day?	1	2	3	4	5	6
10. snore during your sleep?	1	2	3	4	5	6
11. take naps (5 minutes or longer) during the day?	1	2	3	4	5	6
12. get the amount of sleep you needed?	1	2	3	4	5	6

## Attachment 2 Epworth Sleepiness Scale

How likely are you to doze off or fall asleep in the following situations, in contrast to feeling just tired? This refers to your usual way of life in recent times. Even if you have not done some of these things recently, try to work out how they would have affected you.

Use the following scale to choose the most appropriate number for each situation:

- 0 = Would **never** doze
- 1 = **Slight** chance of dozing
- 2 = **Moderate** chance of dozing
- 3 = **High** chance of dozing

SITUATION	CHANCE OF DOZING
Sitting and reading	_____
Watching TV	_____
Sitting, inactive in a public place (e.g. a theatre or a meeting)	_____
As a passenger in a car for an hour without a break	_____
Lying down to rest in the afternoon when circumstances permit	_____
Sitting and talking to someone	_____
Sitting quietly after lunch without alcohol	_____
In a car, while stopped for a few minutes in traffic	_____
Total Score:	_____

